We will now describe how each imputed dataset will be analysed. The choice of analytical approach was determined by both the type of measurement of the outcome (e.g., binary or continuous) and the number of repeated assessments (i.e., number times that these outcomes were measured). These attributes for the outcomes are summarised in Table 1. See the trial protocol paper for more information about outcomes in the trial and their measurement properties (McEvoy et al., 2017).

Table 1

Measurement Properties and Repeat Assessments for Outcomes under Analysis

Outcome	Type of Measurement	Number of Measurements	
		Baseline	Post-Baseline
Primary			
SIAS	Continuous	2	5
SCID-5 Diagnostic Status	Binary	1	2
Clinician Rated Severity	Ordinal (Ranges 0 – 8)	1	2
Secondary			
SPS	Continuous	1	5
BFNE-S	Continuous	1	13
FPE	Continuous	1	13
PROMIS Anxiety	Continuous	2	13
PROMIS Depression	Continuous	2	13

All outcomes aside from SCID-5 diagnostic status, clinician-rated severity, and reliable and clinically-significant change will be analysed using Linear Mixed Models (LMM), as implemented in the R package nlme (Pinheiro, Bates, DebRoy, Sarkar, & R Core Team, 2019). There are some aspects of these analyses that will be the same for all outcomes and some that will differ depending on the number of measurement times for each outcome. The analytical decisions that are the same for all outcomes will be described first, followed by separate sections detailing the decisions individual to each analysis. A summary of the analyses and parameterizations of each is presented at the end.

Accounting for Nesting Within Group

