analyses with outcomes measured at 13 assessments can account for the autocorrelated nature of the residuals without requiring the estimation of as many parameters as would be required with an unstructured matrix. Analyses of pilot data suggest using a heterogeneous CAR1 structure to model the residual errors fits the data better than any of the other correlation structures available in R's nlme package (Pinheiro et al., 2019).

Binary Outcome with 2 Post-Baseline Measurements (SCID-5 Diagnosis)

As all individuals will have a diagnosis of SAD at the baseline assessment, no additional information is gained by including baseline diagnosis in the model. As such, the analysis of change in diagnostic status will only include the diagnoses at the 1-Month and 6-Month follow-ups. To determine whether the proportion of individuals with a SAD diagnosis at the 1-Month and 6-Month follow-ups is significantly different between the treatment groups, a pooled test of the difference in proportions will be carried out.

For each of the imputed datasets, the proportion of individuals in each treatment arm (IE-CBGT & VB-CBGT) with a diagnosis of SAD, and the standard error of that proportion, will be estimated. The difference in proportions, as well as the standard error of that difference, will also be estimated. These estimated proportions and standard errors for each imputed dataset will then be pooled using Rubin's Rules (van Buuren, 2018). These pooled results will give the percentage of individuals in each arm meeting diagnostic criteria at the 1-Month and 6-Month follow-ups, the difference between the arms, confidence intervals for difference, and the significance of the difference.

Ordinal Outcome with 2 Post-Baseline Measurements (Clinician-Rated Severity)

Because clinician-rated severity is an ordinal outcome (rated by category and the categories are ordered in severity) measured on multiple occasions, the analysis will use a cumulative-link mixed-effects model (CLMM) as implemented in the R package 'ordinal' (Christensen, 2019). The CLMM is an extension of the generalised linear mixed-model for use with ordinal data. Baseline severity will be included as a covariate and time will be entered as categorical. A random intercept for each group will be included, but as with the previous analyses will be removed if it shows little variance. To account for the correlation between one- and six-month follow up assessments, a random slope for patient will be used.

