A key concern with the analysis of ordinal data is whether there are sufficient numbers of individuals at each of the rating categories. If there are only a small number of

individuals within a given severity rating, the estimated relationships could be easily influenced by outlying, or simply unrepresentative, responses. This is likely to be the case for the largest and smallest ratings of severity. If severity categories have low numbers of endorsements (< 5), those categories will be collapsed.

It should be noted that the CLMM relies on the assumption of proportional odds. This assumption implies that the effect of the covariates (e.g., treatment) are the same for every category. In other words, regardless of whether the individual has a high or low severity rating, their probability of changing category after receiving treatment is the same. If this is not the case, the resulting estimates of treatment effect are likely to be biased. An alternative is to estimate a different effect for each category. While this is more flexible, and does not assume proportional odds, it also requires estimating more parameters. The analysis of clinician-rated severity will first be carried out assuming proportional odds. The proportional odds assumption will then be evaluated. If there is a substantial departure from proportional odds for a given covariate, the analysis will be refitted with non-proportional odds for that covariate.

Reliable and Clinically Significant Change (SIAS)

Beyond simply testing whether the amount of change in social anxiety symptoms is statistically significant, it is also of interest to examine whether those changes are: a) beyond what would be expected due to measurement error, and b) clinically meaningful. This is the examination of reliable and clinically significant change (RC and CSC, respectively) described by Jacobson and Truax (1991). The analyses will examine the RC and CSC of the SIAS using the multiply-imputed datasets.

The calculation of RC is defined as:

$$RC = \frac{(SIAS_{pos} - SIAS_{pre})}{\sqrt{2 * SE^2}}$$

Where:

$$SE = SD_{pre} * \sqrt{1 - r}$$

Where r is the reliability of the SIAS. For this analysis, the previously described McDonald's Omega coefficient will be used as the estimate of the reliability of the SIAS. If

$RC > 1.96$, this indicates that the amount of change is greater than can be attributed to measurement error.

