A key sensitivity analyses will be testing the sensitivity of the results to violations of the missing at random (MAR) assumption. As multiple imputation assumes that the data are MAR, the imputed values could be biased if this is not the case. In other words, if there is a systematic reason for why some individuals did not adhere to treatment, ignoring this when imputing their missing responses could bias the results away from the ‘true’ effect. A common means of testing this assumption is called a ‘tipping-point’ analysis (Mallinckrodt & Lipkovich, 2017). The tipping-point approach to sensitivity analysis is implemented by modifying the imputed data by increasing amounts and identifying the magnitude of changes in imputed data that would be required for the results to no longer be significant (Mallinckrodt & Lipkovich, 2017). This is achieved through the repeated use of what is called a ‘delta-adjustment’ of the imputed values (van Buuren, 2018). A delta-adjustment is simply the addition of a fixed value (delta) to every imputed response. In other words, this approach is

artificially raising or lowering the mean response of all non-adherent individuals. By using increasingly large values of delta (the fixed value), a sensitivity analysis can identify the extent to which the non-adherent individuals would need to differ in their response before there is no longer a significant difference between the treatment groups.

Summary of Confirmatory Analyses

Outcome	Analysis	Fixed Effects	Random Effects	Residual Covariance Structure
SPS & SIAS	Linear Mixed Model	
 • Baseline • Time (Categorical) • Treatment • Baseline*Time • Treatment*Time 	
 • Intercept (Group) 	
 • Unstructured • Heterogenous Variances
BFNES, PROMIS Anxiety & Depression	Linear Mixed Model	
 • Baseline • Time (Piecewise) • Treatment • Baseline*Time • Treatment*Time 	
 • Intercept (Group) 	
 • CAR1 • Heterogenous Variances
Diagnostic Status	Pooled Test of Difference in Proportions	N/A	N/A	N/A
Clinician-Rated Severity	Cumulative-Link Mixed Model	
 • Baseline • Time (Categorical) • Treatment • Baseline*Time • Treatment*Time 	
 • Intercept (Group) • Intercept • Time 	N/A

References

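### The only planned test of departures from MAR adds a constant to imputed values, which is invalid for SCID-5 diagnosis and at best rough for clinician-rated severity

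*SAP*

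**What the plan says.** Under Diagnostic Checks, Sensitivity, and Alternative Analyses, the Multiple Imputation section states: "A key sensitivity analyses will be testing the sensitivity of the results to violations of the missing at random (MAR) assumption". The method is a tipping-point analysis using delta-adjustment, defined as follows: "A delta-adjustment is simply the addition of a fixed value (delta) to every imputed response". The section describes the effect as "artificially raising or lowering the mean response of all non-adherent individuals". Delta is increased until the difference between arms is no longer significant. The text does not limit this to any type of outcome.

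The table of measurement properties under Confirmatory Longitudinal Analyses shows that two of the three primary outcomes are not continuous. One row reads "SCID-5 Diagnostic Status Binary 1 2". Clinician-rated severity is listed as "Ordinal (Ranges 0 – 8").

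Both are analysed on imputed data:
- **Diagnosis.** Each imputed dataset supplies "the proportion of individuals in each treatment arm (IE-CBGT & VB-CBGT) with a diagnosis of SAD, and the standard error of that proportion". These are then pooled by Rubin's Rules.
- **Severity.** A cumulative-link mixed model is fitted, with the rule "If severity categories have low numbers of endorsements (< 5), those categories will be collapsed".

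Imputation Software and Settings names predictive mean matching for the missing data and gives no separate method for binary or ordinal outcomes.

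**The concern.** Under the de jure estimand, data collected after a patient becomes non-adherent are not used. Primary hypotheses (b) and (c), on diagnosis and clinician-rated severity at one month, therefore rest on imputed outcomes for every patient who became non-adherent before then. Whether those results survive a departure from MAR is the question the key sensitivity analysis is meant to answer.

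Adding a constant has a clear meaning on a continuous score. It has none on a 0/1 code. On an ordinal rating it has meaning only under conditions that the SAP does not set. If the rule is followed as written, a claim of robustness for (b) has no valid basis, and a claim for (c) depends on choices made after the data are seen. The scale of the shift, the step size and the handling of values beyond the ends of the scale are substantive decisions that a SAP should settle in advance.

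**Working it through.** **Inputs from the SAP:** the additive rule; diagnosis coded as binary; severity ordinal from 0 to 8; diagnosis analysed as a proportion with its standard error; severity analysed by a cumulative-link model.

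**Assumed inputs:** the SAP gives neither the SAD rate at one month nor the share imputed. I take SAD rates p from 0.30 to 0.80 and imputed shares m from 0.10 to 0.40, with the same SAD rate among imputed and observed patients before any shift. There is no figure in the plan to reproduce.

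**Step 1: diagnosis, the values produced.** Imputed 0 and 1 become delta and 1 + delta.

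| delta | 0 becomes | 1 becomes | valid codes |
|---|---|---|---|
| 0.1 | 0.1 | 1.1 | none |
| 0.25 | 0.25 | 1.25 | none |
| 0.5 | 0.5 | 1.5 | none |
| 1 | 1 | 2 | first only |

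No non-zero delta leaves both codes valid.

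**Step 2: diagnosis, the arm proportion.** If the shifted codes are averaged, the proportion is (1 − m)p + m(p + delta) = p + m × delta, and the usual variance term is that value times one minus itself.

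| p | m | delta | proportion | variance term |
|---|---|---|---|---|
| 0.50 | 0.30 | 0.25 | 0.575 | 0.244 |
| 0.50 | 0.30 | 1 | 0.80 | 0.16 |
| 0.80 | 0.20 | 1 | 1.00 | 0 |
| 0.80 | 0.30 | 1 | 1.10 | 1.10 × (−0.10) = −0.11 |
| 0.80 | 0.40 | 1 | 1.20 | 1.20 × (−0.20) = −0.24 |

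The proportion exceeds 1 once delta is greater than (1 − p)/m. For p = 0.80 and m = 0.30 that is 0.20/0.30 = 0.67. For p = 0.50 and m = 0.30 it is 0.50/0.30 = 1.67. The breakdown in range therefore depends on the assumed rates, but the invalid codes in Step 1 do not.

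**Step 3: severity, fractional delta.** For any delta strictly between 0 and 1, an imputed rating k moves to a point between k and k + 1. The order of all ratings, and the number at each distinct value, are the same for every such delta. A cumulative-link model uses only that order, so the fit does not change as delta increases within the interval. For example, delta 0.5 puts all nine ratings (0.5, 1.5, … 8.5) off the defined categories.

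**Step 4: severity, whole-number delta.** Delta 1 sends the top rating to 9. Delta 2 produces 9 and 10, and delta 3 produces 9 to 11, all outside 0 to 8. A fixed step also treats the categories as equally spaced, an assumption the ordinal model avoids.

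**Step 5: diagnosis on the log-odds scale, for comparison.** The arm rate is (1 − m)p + m × expit(logit(p) + delta), with m = 0.30.

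| p | delta 0 | 0.5 | 1 | 2 | every imputed patient has SAD |
|---|---|---|---|---|---|
| 0.30 | 0.300 | 0.334 | 0.371 | 0.438 | 0.51 |
| 0.50 | 0.500 | 0.537 | 0.569 | 0.614 | 0.65 |

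For p = 0.80 the odds are 4. With delta 1 they become 4 × 2.718 = 10.87, a probability of 0.916, so the arm rate is 0.56 + 0.30 × 0.916 = 0.835, against 1.10 under the additive rule. The upper bound is 0.56 + 0.30 = 0.86. The result is always a valid proportion, and it moves gradually with delta.

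**The case against.** The strongest reply is that the tipping-point paragraph is explanatory. It speaks of a mean response, never says that the method will be run on diagnosis or severity, and cites a textbook for delta-adjustment. A competent analyst would not add 0.2 to a diagnosis. This has some force as a reading of intent. However, the paragraph defines the adjustment itself, tests the results without restricting them by outcome, and gives no alternative for the two outcomes. If it was meant for continuous scales only, diagnosis and severity have no planned test of departures from MAR at all.

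Other parts of the reply stand and limit the point:

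- **Other checks exist.** A reader might infer that imputation for these two outcomes goes unchecked. The SAP does not support that. It lists checking the imputations as a step, gives remedies for implausible ones, and compares imputed with observed-data results for each model. None of these tests departures from MAR, and the SAP itself says that a marked difference in the last comparison could mean either faulty imputation or bias that imputation has corrected.
- **Severity is not beyond use.** A reader might infer that any shift in severity is meaningless. Whole steps held within 0 to 8 would be a rough but readable stress test, and the collapsing rule could absorb a few ratings above 8. The SAP specifies neither the whole steps nor the limits.
- **SIAS is not the only outcome covered.** SPS, BFNE-S, FPE and both PROMIS scales are continuous, and delta can be added to SIAS before reliable and clinically significant change is classified. The restriction to SIAS applies among the primary outcomes only.
- **The consequence is bounded.** The tipping point, as defined, is sought where a significant difference exists, and the primary estimates do not depend on it.

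**Conclusion.** The point holds as a defect in the specified sensitivity analysis. For SCID-5 diagnosis the stated rule is invalid at every non-zero delta because of the outcome's type, whatever the missingness. The proportion of 1.10 illustrates how far it can go under an assumed 80% SAD rate, 30% imputed and delta 1. At lower SAD rates the proportion can stay within range while still being built from codes that are not diagnoses. For clinician-rated severity the rule gives no graded stress at fractional deltas and leaves the scale at whole-number deltas, so a usable version would need choices that the SAP does not make.

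Among the primary outcomes, the planned test of departures from MAR works properly only for SIAS. The SAP does not support the stronger conclusions that the primary estimates are wrong or that the imputations for diagnosis and severity receive no checks. The change should be made before the sensitivity analysis is run.

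**What to change.** Amend the tipping-point paragraph to state the scale of the shift for each type of outcome:

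- **Continuous outcomes:** keep the additive delta.
- **SCID-5 diagnosis:** impute with a logistic model, since predictive mean matching draws observed values and offers no log-odds to shift, and apply delta on the log-odds scale. Alternatively, present a two-way tipping table showing how many imputed results of no SAD in each arm are changed to SAD. The extreme case is that all imputed patients keep the SAD diagnosis that everyone had at baseline. Choose one in advance.
- **Clinician-rated severity:** apply the shift on the cumulative-logit scale, multiplying the odds of a higher rating by a set factor, and redraw ratings within 0 to 8.

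The cost is SAP wording and modest programming. No new data are needed, and the primary estimates are unchanged.

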In short, the study is a superiority trial that aimed to randomise at least 96 individuals with social anxiety-disorder to one of two 12-week group treatments for SAD (IE-GCBT and VB-GCBT). There is also a one-month follow up group review session. Over 20 outcome measures have been collected at various times before, during, and after treatment. The primary endpoint is the one month follow up (i.e., coinciding with the follow up group review session). This was selected on the basis of pilot data which showed differences between the treatments are larger at one-month follow up than at the end of weekly treatment sessions (McEvoy et al., 2015). No interim analyses or stopping rules were planned, nor have any been used.

The primary hypotheses are that, at the one-month follow up, IE-GCBT will be superior to VB-GCBT in terms of (a) reduction in severity of self-reported social anxiety symptoms (b) percentage of individuals with a SAD diagnosis (c) reduction in clinician-rated severity of social anxiety symptoms. McEvoy et al. (2017) also describe a wide range of additional hypotheses concerning secondary outcome measures, mechanisms of change, and moderation. Given the numerous outcomes and possible research questions, it is not possible to comprehensively report them all in a single paper. Therefore, they will be addressed across several publications.

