The criteria for having achieved CSC were the same as described in previous pilot research (McEvoy et al., 2015). Individuals were required to have scored above a severity cut-off before treatment, achieved RC, and subsequently scored below the cut-off after treatment. The severity cut-off was defined as the mid-point between the clinical and normative means reported by Carleton et al. (2014), which was 40.56 for the SIAS.

To determine whether the proportions of individuals achieving reliable and/or clinically significant change significantly differed between treatment arms, a pooled test of the difference in proportions was carried out (the same procedure described for the analysis of diagnostic status).

Contrasts for Continuous and Ordinal Outcomes

The primary hypotheses are concerned with whether there are differences between the treatments at one month follow up. In order to determine this, for each continuous and ordinal outcome, the data from all the measurement occasions are jointly modelled using a LMM (rather than say, only using the one-month follow-up data in the analysis; see Mallinckrodt and Lipkovich (2017)). We will then use contrast coefficients to (i) estimate the marginal means for each treatment at each measurement occasion, and (ii) compute the mean difference between treatments and a standard error at the one-month follow up time point. For continuous and ordinal outcomes, we will compute the contrasts using R's emmeans package. For the ordinal outcome this contrast is an odds ratio, representing the difference in probability of belonging to a higher severity rating between the two treatment arms.

Evolution of Outcomes Over Time

A secondary goal of this paper is to understand how differences between the groups evolve over time. Analyses of pilot data suggest these tend to be smaller at post-treatment than at one-month follow up. We have no pilot data for the six-month follow up. Therefore, we will use additional contrasts to examine differences between the treatments at week 12 (end of weekly treatment sessions) and the 6-month follow up. This will provide valuable information about the evolution of treatment outcomes before and after the primary endpoint.

Reporting of Results

Analysis Code and Output

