All analysis code and output will be uploaded to the Open Science Foundation. This will ensure that all results are replicable, and that other scholars can easily extend our work. In the paper itself, we will summarise the key findings.

Standardized Effect Size

For continuous outcomes, we will convert the mean difference between groups into a standardised effect size by dividing the difference by the pooled pre-treatment standard deviation. We will also compute standardized within-group effect sizes, by subtracting the mean baseline score from each treatment's estimated marginal mean at the one-month follow up and dividing by the pooled pre-treatment standard deviation. For binary outcomes, the difference in proportion is an effect size. For ordinal outcomes, the odds ratio is an effect size.

Confidence Intervals

For each outcome, we will report a 95% confidence interval for the difference between groups at one-month follow up.

P-values

There have recently been calls to reform or abandon significance testing (for more details, see a recent special issue of the American Statistical Association's *American Statistician* journal [here](#)). In the present paper, we will report p-values continuously (e.g., $p = .078$) rather than just reporting whether they are less than or greater than .05.

Multiplicity

Due to the moderate sample size, there is a greater risk of Type II errors than Type I errors in the current trial. All hypotheses are also prespecified and the number of outcomes being analysed is limited. Therefore, no adjustment for multiplicity will be used.

Diagnostic Checks, Sensitivity, and Alternative Analyses

Model Assumptions

The graphical 'lineup' procedure will be used to assess the model assumptions of residual normality and normality of random effects for the mixed-model analyses of continuous and

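### The tipping-point analysis, as written, shifts imputed values in both arms by one common delta, so with similar missingness it overstates robustness to worse outcomes among IE non-adherers

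*SAP*

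**What the plan says.** The text is in the SAP, Diagnostic Checks, Sensitivity, and Alternative Analyses, under Multiple Imputation. It opens: "A key sensitivity analyses will be testing the sensitivity of the results to violations of the missing at random (MAR) assumption". The adjustment is then defined: "A delta-adjustment is simply the addition of a fixed value (delta) to every imputed response". The next sentence describes the effect as "artificially raising or lowering the mean response of all non-adherent individuals". Delta is increased to find how far non-adherent participants "would need to differ in their response before there is no longer a significant difference between the treatment groups".

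No section sets a delta by arm, a grid of delta pairs, a leading direction or a range, and no other missing-not-at-random analysis is specified. The estimate being challenged is the one in Contrasts for Continuous and Ordinal Outcomes, where the analysts will "compute the mean difference between treatments and a standard error at the one-month follow up time point".

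Two other parts of the SAP bear on this. Under Estimand, data are used only until a participant becomes non-adherent, so later values are imputed in either arm. In the table of measurement properties, "SCID-5 Diagnostic Status" is binary and clinician-rated severity is ordinal from 0 to 8; both are primary outcomes.

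**The concern.** In a superiority comparison, the departure from missing at random that matters most is one that differs between arms, with participants who stopped IE doing worse than imputed while those who stopped VB did not. A delta common to both arms assumes that the two sets of missing values depart equally. Most of the shift then drops out of the between-arm difference unless the arms have very different amounts of missing data. A large tipping delta could be reported as strong robustness when it mainly reflects how much the shift widened the within-arm spread.

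Because values after non-adherence are imputed by design, and this is the only check on that assumption, a reader would rely on it to judge a positive primary result.

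**Working it through.** The SAP states no effect size, SD, dropout rate or delta range, so there is no figure of its own to reproduce. The calculation below shows the size under stated assumptions.

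**Inputs from the SAP**
- The trial aimed to "randomise at least 96 individuals with social anxiety-disorder to one of two 12-week group treatments".
- Confidence level: "we will report a 95% confidence interval for the difference between groups at one-month follow up". I take two-sided 5% (z = 1.96) as the significance criterion.
- Delta is common to all imputed values, as quoted above.

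**Assumptions**
- n = 48 per arm (the SAP does not give the allocation ratio); a continuous outcome with SD = 1; higher is worse.
- Effect under missing at random: d = 0.6 SD, varied from 0.5 to 0.7. With 48 per arm, 80% power is reached at about 0.58 SD.
- Imputed share at one month: m_IE and m_VB, from 10% to 35%.
- A two-sample approximation, without the mixed model's baseline adjustment or group intercept.

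**Step 1: movement of the estimate.** With d the benefit of IE and delta > 0 meaning worse:
- common delta: difference = d − delta × (m_IE − m_VB)
- IE-only delta: difference = d − delta × m_IE

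Per 1 SD of common delta, the IE benefit falls by 0.00 SD at equal missingness, 0.05 at 25% IE against 20% VB, 0.10 at 30/20 and 0.20 at 35/15. At 20/30 it rises by 0.10. With an IE-only delta it falls by m_IE, that is 0.10 to 0.35 SD.

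**Step 2: variance.** The contribution of each arm is [1 + m(1 − m) × delta²]/n + [1/(n(1 − m)) − 1/n]. The delta² term is the extra spread created by shifting some values and not others; it is absent from an unshifted arm. The second bracket approximates imputation uncertainty.

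**Step 3: tipping point.** Find the smallest delta at which difference/√variance falls below 1.96.

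Worked case, 20% in each arm, d = 0.6:
- Common, delta = 2.50: the difference stays 0.6. Variance = 2 × (1 + 0.16 × 6.25)/48 + 2 × (1/38.4 − 1/48) = 0.0833 + 0.0104 = 0.0938. z = 0.6/0.3062 = 1.96.
- IE only, delta = 0.73: difference = 0.6 − 0.2 × 0.73 = 0.454. Variance = (1 + 0.16 × 0.533)/48 + 1/48 + 0.0104 = 0.0539. z = 0.454/0.232 = 1.96.

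Results at d = 0.6 SD, worsening deltas:

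| Imputed IE / VB | Common delta | IE-only delta | Ratio |
|---|---|---|---|
| 10% / 10% | 3.56 | 1.58 | 2.3 |
| 20% / 20% | 2.50 | 0.73 | 3.4 |
| 30% / 30% | 1.98 | 0.40 | 5.0 |
| 30% / 20% | 1.04 | 0.45 | 2.3 |
| 35% / 15% | 0.62 | 0.38 | 1.6 |
| 20% / 30% | 7.16 | 0.66 | 10.8 |

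In the three equal-missingness rows the estimate never moves. If the delta² term is removed, neither numerator nor denominator depends on delta and no tipping point exists. In the last row the apparent IE benefit grows with delta.

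**Step 4: other effect sizes** (10%, 20%, 30% imputed in each arm, common against IE-only):
- d = 0.5: 2.24 v 0.74, 1.40 v 0.26, 0.80 v 0.08
- d = 0.7: 4.66 v 2.34, 3.37 v 1.17, 2.79 v 0.72

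The direction is the same throughout. The ratio is about 2 to 4 at 0.7 SD (4.66/2.34 = 2.0; 2.79/0.72 = 3.9) and about 3 to 10 at 0.5 SD (2.24/0.74 = 3.0; 0.80/0.08 = 10), where the starting result is already borderline.

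**The case against.** The sentence that fixes the delta is partly a textbook definition, and the analysts may have meant to vary delta by arm. That is possible, but it is the only specification, and the sentence after it applies the shift to all non-adherent participants. Someone following the text would shift both arms.

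A reader might infer that the shift always cancels, or that the analysis can never show a threat to superiority. The SAP does not support that, because it gives no dropout rates. When IE has clearly more missing data, a common worsening delta does reduce the IE benefit: at 35/15 the two tipping deltas are 0.62 and 0.38 SD.

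A reader might also infer one fixed multiple of overstatement. There is none. At 0.5 SD with 25% imputed in each arm, the ratio is about 4.5 (1.67 v 0.37 SD) using sampling variance alone and about 7 (1.10 v 0.15 SD) once imputation uncertainty is added.

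The plan allows lowering as well as raising. At 20/30 and 0.6 SD, a common lowering delta tips at about −1.04 SD, so the 7.16 SD in the table covers worsening only. This stands, but lowering means that missing participants did better than imputed, which is not the threat at issue.

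That the method has little to say when the main result is not significant is an ordinary feature of tipping-point analyses and is no fault of this plan. Nor does the SAP say outright that a fixed number will be added to a yes/no diagnosis; it leaves the scope open.

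Finally, this is a sensitivity analysis and alters no primary estimate, interval or p-value. That limits the severity.

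**Conclusion.** The point holds as a conditional one. As written, the SAP applies one delta to imputed values in both arms. The between-arm difference then moves only with the difference in imputed shares: not at all if these are equal, and in favour of IE under a worsening delta if VB has more missing data. With similar missingness, a natural planning assumption for two group therapies of the same length and format, the tipping delta reflects mainly variance inflation. It is then too large as a measure of robustness to worse outcomes among IE non-adherers alone.

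Under the assumptions above the overstatement is about 2.3- to 5-fold with equal missingness at 0.6 SD, and about 1.6-fold at 35/15. The direction follows from algebra. The size depends on dropout and effect sizes that the SAP does not give.

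This should be fixed, but it does not undermine the primary analysis: the check matters chiefly if a primary result is significant, and the primary estimate is the same either way.

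**What to change.** In the sensitivity subsection on multiple imputation:

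- **Continuous outcomes.** Apply delta separately by arm, either to imputed IE values only or over a two-way grid of IE and VB deltas. State the range and direction before unmasking. Report the one-month difference and its 95% CI across the grid, not only the tipping value.
- **SCID-5 diagnosis.** Adding a fixed number is not meaningful here. Vary the proportion with a diagnosis among imputed cases, separately by arm.
- **Clinician-rated severity.** Use whole-category shifts kept within 0 to 8, separately by arm.
- **Masking.** Run the analysis with each coded arm in turn as the one that is worsened, so that the analyst can stay masked as the SAP intends.

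The categorical changes act on values already imputed, so the planned predictive mean matching can stay. A delta on the log-odds scale would need a different imputation method.

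The cost is SAP wording, a modest amount of code, and refitting the models to the 100 imputed datasets at each grid point. No new data are needed.
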